5. STUDY SITES AND POPULATION

a. Study Sites

The evaluation will be conducted nationally in Malawi. Data collected may pertain to the entire national cohort of ART patients (e.g. Baobab Health NART) or to specific smaller cohorts developed by implementing partners, other researchers, and clinics themselves.

b. Inclusion Criteria

This study aims to measure coverage and outcomes of DSD across Malawi. For this reason, we will include in our study all adults who are accessing care for HIV anywhere in the country. The inclusion criteria are shown below.

Inclusion criteria

- ≥ 15 years old
- Patients accessing care for HIV within the data collection period (January 1, 2014 to February 28, 2021)
- In any HIV transmission risk group (general adults and adolescents, high transmission risk populations)

Exclusion criteria

None

Children younger than 15 are excluded from this study for two reasons. First, they are typically treated in pediatric HIV programs that have different drug regimens, visit schedules, and models of care than do adults. Second, the vast majority of DSD implementation in the focus countries to date has involved only adult and adolescent patients, not children [15].

6. DATA SOURCES AND MANAGEMENT

a. Data Sources

The MOH and its partners will implement the DSD strategies addressed in this study. This protocol is solely for an evaluation of the coverage and outcomes of the interventions. The study team will have no involvement in providing services nor any interaction with patients. The evaluation will instead rely solely on existing, retrospective national-, facility-, and patient-level records.

Routine data sources to be accessed for this study include:

- Baobab Health National ART (NART) System
- Baobab Health Laboratory Information Management Systems (LIMS)
- Other MOH electronic and paper patient records and registers which capture relevant information related to the care and treatment of patients in any model of ART care and treatment. NART does not currently fully capture model of service delivery, for example, so access to paper files at clinics may be required to build the study database.
- Existing, de-identified data sets from trial, cohort, and observational studies, in collaboration with implementers, technical support partners, and research organizations.

The Ministry of Health will be asked to assure and facilitate access to Baobab Health's NART, LIMS and other routinely collected sources of electronic data.

Data will be collected for all patients in each data set who accessed care for HIV on or after January 1, 2014. The focus countries began large-scale implementation of DSD in 2015 or 2016. Starting in 2014

will thus allow us a pre-intervention period for comparison. Data collection will continue throughout the study period, which ends on February 28, 2021.

b. Data Fields to be Collected

Below (Table 1) we summarize the existing data required for the evaluation. A detailed list of data fields follows this summary.

Table 1. Data sought for evaluation of DSD

Themes	Potential availability and source(s)
Proportion of current ART patients meeting definition	Data from electronic medical records, existing M&E reports, IeDEA
of stable; distribution of reasons for not meeting	and PEPFAR partners, cohorts under observation, facilities
definition	participating in others' studies
Geographic distribution and description of	Reports from existing implementers and technical support
differentiated models in use	partners and MOH
Number (proportion) of patients in each model at time	Data from existing implementers and technical support partners,
of data collection; patient-months enrolled in each	with quality assessment through primary data collection at a
model in previous 12-month period	sample of sites
Location, duration, and frequency of dispensing for	Electronic medical record data; pharmacy data
ARVs and other ART-related medications (e.g. INH)	
Number of facility and non-facility visits per patient	Electronic medical record data
per year, by model of care and purpose of visit (e.g.	
clinical consultation, medication pickup)	
Number and outcomes of viral load tests, CD4 counts,	Electronic medical record data
and other ART-related laboratory assays per patient	
per year, by model of care	

The specific data fields available and required for different patient types will vary slightly (e.g. viral loads will not be available for patients newly initiating treatment). In general, however, we will collect a common set of variables for all patients. The specific fields are listed below:

Demographic information

- Electronic medical record system number (e.g. Baobab Health NART record number)*
- Clinic file, register, and card numbers (assigned by the clinic)*
- National ID number*
- Name*
- Date of birth*
- Weight and height or BMI
- Sex
- Age in years
- Marital status if recorded
- Employment status if recorded
- Education level if recorded

· Smoking and alcohol use if recorded

*Identifiers like name and date of birth are required to link electronic and paper-based records pertaining to individual patients. Many clinics use name or initials and date of birth to create a clinic record number. For example, numbers and dates of clinic visits can typically be extracted from Baobab Health, but the specific model of care used by an individual patient may require linking Baobab Health records to data manually transcribed from paper clinic records.

Clinical information

- Date of positive HIV test (if available)
- Dates of all clinic visits (including pre-ART and after ART initiation)
- Primary purpose of all clinic visits (e.g. HIV test, CD4 count, counselling, ARV dispensing, ART monitoring, etc.)
- Dates of next scheduled clinic visits (dates patients are expected to return to clinic)
- Date treatment eligibility determined, if reported
- Date and result of CD4 count indicating treatment eligibility (baseline)
- WHO stage and clinical conditions
- Date and result of TB symptom screen
- Date, type, and result of TB test
- Date TB treatment initiated, if relevant
- Date ART initiated (first dose of medications dispensed)
- First-line regimen prescribed
- Any changes to first line regimens and dates of changes
- Dates, quantity (duration), and type for all medication collections
- Dates and results of all viral load tests
- Dates and results of all other laboratory investigations

DSD information

- Model(s) of care enrolled in and duration of enrollment
- Eligibility criteria and dates for alternative model of care
- Dates of participation in DSD activities (e.g. adherence club attendance, CCMDD pickups, multimonth dispensing, etc.)
- Other resources used for ART and recorded in the data source

In addition, we will collect aggregate, clinic- or DSD-level information about resources utilized, providers accessed, volumes served, etc. **This will not be human subjects research.** We will obtain this information from descriptions included in papers and reports, and, where necessary, surveys conducted by the study team.

c. Data Entry and Storage

The data sets that will be analyzed in this study will be shared with the study team by the Ministry of Health, implementing partners, or other researchers/evaluators. For all patient data extracted from paper files and registers, we anticipate entering all data onto electronic case report forms on tablets on site, so that paper forms do not need to be removed from the study clinics. Once patient information is captured on the tablet, the information will be immediately sent to a highly secure cloud server and wiped from the tablet. Once the databases are received by the study team, the data will be downloaded onto secure, protected drives at the HE²RO office in South Africa and at Boston University, with access limited to relevant study staff. Details on data transfer and drive security are provided under Subject Confidentiality below.

Each subject in a data set will immediately be assigned an anonymous patient ID number. For each subject, a national ID number, electronic clinic record number, date of birth, and name will be collected to allow linking of fields extracted from multiple data sources (registers, records, lab reports, etc.). An electronic linking file will link this information to the patient ID number. The linking file will be kept until all data collection is complete, the data set has been closed, and all data has been linked. Once the linking is complete, the linking file will be destroyed. All data collection files will be coded using patient ID numbers and not contain subject identifiers. We note that some data sets, such as those from completed trials, will be closed (no further updates expected) when we receive them, and these data can be de-linked soon after receipt. Other data sets, like longitudinal electronic medical record data, will not be closed until the study is completed.

Study databases will be managed at the HE²RO Johannesburg office by the study team. On a regular basis, the data will be converted to SAS, STATA, or SPSS for cleaning and data analysis. All data management and analytic databases will be password-protected with access restricted to the members of the study team. All linking files will be destroyed once the analytic data sets are cleaned and closed. De-identified analytic datasets will be provided to the study collaborators to allow participation in analysis.

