7. DATA ANALYSIS

a. Sample Size

In order to measure national coverage of DSD, we will access data for up to the entire national ART cohort. In Malawi, the estimated number of individuals on ART is currently 740,000 [16]. This is expected to increase to \geq 90% of the entire HIV-infected population by the time the study ends. We therefore expect to collect and analyze data for up to 1,000,000 individuals, the estimated HIV-positive population in Malawi [16]. As noted above, all data will be drawn from records that exist at the time of data collection; the study will have no interaction with study subjects.

b. Outcomes

To estimate uptake, benefits, and costs of DSD, we will aim to report the following results, stratified by model care and/or other patient or clinic/model characteristics:

- Percentage of current ART patients eligible for any alternative model, under current guidelines
- 2. Demographic, economic, and clinical characteristics of patients in each model, as data allow.
- 3. Patient-months enrolled in any DSD and in each model
- 4. Frequency of transfer between models of care, including back to the conventional model
- 5. Location, duration, and frequency of ARV dispensing
- 6. Number of clinical visits/patient/year
- 7. Quantities of resources used/patient/year
- 8. Geographic distribution of patients enrolled in each DSD
- 9. Retention on ART, measured at 6-month intervals
- 10. Proportion virally suppressed (< 400 copies/ml³)
- 11. Other outcomes relevant to DSD that can be estimated from available data

Note: as this is not a clinical trial, we have not designated primary and secondary outcomes. We will report as many of the above outcomes as data allow.

c. Analysis

To evaluate the broad, national- or system-wide implications of differentiated models of ART delivery in the context of health systems in sub-Saharan Africa, we will conduct the following analyses.

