Outcomes 9-11 measure health outcomes by model of care. For these outcomes, we will begin with descriptive analyses of the characteristics of the population stratified by model of care. For each outcome described above, we will conduct a crude analysis comparing the proportion of subjects with the outcome by model of care. Next, we will conduct an analysis for each outcome accounting only for clustering using generalized estimating equations (GEE) with an unstructured correlation matrix and clustering by treatment site. In all cases the outcomes are dichotomous and therefore we will calculate risk differences comparing the intervention to the comparison arms using a linear link function and a binomial distribution. Next, should any imbalances between models of care be detected, we will adjust for those covariates in our GEE model. Finally, we will look for differences in the effects of the models of care by important baseline characteristics (e.g. size of the treatment population, rural vs. urban, province, etc.) using stratified analyses.

d. Dissemination of Findings

The results of this study will be disseminated as widely as possible in the study countries and globally. A full report will be made to local stakeholders and will be circulated widely and posted on our website. We will also develop a short briefing document to send to the Ministry of Health, donor agencies, and other interested organizations, and we will present the results at relevant conferences domestically and internationally. One or more journal manuscripts will be submitted to an appropriate peer-reviewed international journal.

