The indirect benefits of this study are expected to be large. Differentiated service delivery models are being scaled up across sub-Saharan Africa and will ultimately affect hundreds of thousands, if not millions, of patients. Generating information about coverage, allocation, costs and benefits of these programs has the potential to make the DSD models more effective nationwide. The evaluation will also assist the MOH to target and tailor its interventions and allocate its resources to the patients at greatest need and/or most likely to benefit and help project budgetary needs in future years.

e. Risk to Benefit Ratio

Because the indirect benefits of the study are large and the risks to human subjects are minimal, we are confident that the risks to subjects are reasonable in relation to anticipated benefits.

f. Recruitment Procedures

As explained above, we will not generate any new (not yet collected) data for this study, nor will we have any interaction with study subjects. We will therefore not have an active recruitment procedure. We will enroll in the study all current and former ART patients accessing HIV care from January 1, 2014 to February 28, 2021. No screening of study subjects will be conducted.

g. Informed Consent

We do not intend to seek informed consent for this study which is a retrospective record review only and poses minimal risk to study subjects. We therefore request a Waiver of Informed Consent.

h. Subject Confidentiality

As explained above, we will take multiple steps to protect subject confidentiality. These are detailed in the paragraph entitled "Potential Risks and Protections."

i. Destruction of Identifiers

The linking files will be kept until all data collection for each individual study subject is complete, the data set has been closed, and all data has been linked. Once the linking is complete, the linking file will be destroyed. All data collection files will be coded using patient ID numbers and not contain subject identifiers. We note that some data sets, such as those from completed trials, will be closed (no further updates expected) when we receive them, and these data can be de-linked soon after receipt. Other data sets, like longitudinal electronic medical record data, will not be closed until the study is completed, as we anticipate receiving updated EMR data sets periodically throughout the project.

j. Costs and Payments

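### Entry by care contact from 2014, with no limit on ART start date, left-truncates earlier starters; retention counted from ART start, or from pre-2014 entry to conventional care, would be inflated

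*Protocol*

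**What the plan says.** Section 6a sets the entry rule: "Data will be collected for all patients in each data set who accessed care for HIV on or after January 1, 2014". Section 5b uses the same window as an inclusion criterion, and section 8f repeats it: "We will enroll in the study all current and former ART patients accessing HIV care from January 1, 2014 to February 28, 2021". None of the three limits the date of ART initiation.

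Section 6a also gives the reason for the date. "The focus countries began large-scale implementation of DSD in 2015 or 2016", so beginning in 2014 "will thus allow us a pre-intervention period for comparison".

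The fields in section 6b include the date of ART initiation and "Dates of all clinic visits (including pre-ART and after ART initiation"), with no stated lower limit on the visit dates.

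Outcome 9 in section 7b is "Retention on ART, measured at 6-month intervals". No time origin is given. For Outcomes 9-11, section 7c says "we will conduct a crude analysis comparing the proportion of subjects with the outcome by model of care". It then describes GEE risk differences clustered by site, adjustment for covariates if imbalance between models is found, and stratified analyses. No step provides for delayed entry, a landmark, or restriction to patients who started ART within the window.

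**The concern.** The entry rule conditions on a care contact in 2014 or later. Someone who began ART in 2008 is in the data only if they were in care, or returned to it, after that date. Those who began alongside them and left permanently are missing. This is left truncation, and it would be present even if every patient were in conventional care.

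A simple proportion takes no account of it. Counted from ART start, the early months of pre-2014 starters are observed only in people already known to have come through them. Section 3a itself describes the time just after initiation as one of high mortality and loss, so the missing losses are concentrated in the earliest intervals.

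Two things are at stake. One is the level of early retention. The other is the comparison of models, if they hold different shares of long-standing patients. Section 3b expects little short-term health gain but says that differentiated service delivery (DSD) may affect long-term retention, so retention is an outcome on which the evaluation could turn. With up to 1,000,000 records, a false difference would look precise.

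**Working it through.** The protocol states no retention figure, attrition rate or distribution of ART start dates, so it has no figure to reproduce. The rule and the estimator come from the protocol; every rate below is an assumption.

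**Assumptions.** Retention in year 1 is 80% (range 70-90%) and 95% a year afterwards (range 90-95%). ART starts occur at a constant rate over A years before 2014 and 6 years after. No one returns after being lost. With t in years since ART start, S(t) = 0.80^t up to one year and 0.80 × 0.95^(t−1) after that.

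**One start year.** For a start at the beginning of 2008, the share in the data is S(6) = 0.80 × 0.95^5 = 62%. All of them have passed month 12, so observed 12-month retention is 100% against a true 80%.

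**Pooled over start years.** Per unit start rate, the pre-2014 starters included are N = ∫₀^A S(u)du, and those retained at 12 months are R = 1 × S(1) + ∫₁^A S(u)du. The two pieces are:

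- ∫₀¹ S = 0.20/0.2231 = 0.896
- ∫₁^A S = 0.80 × (1 − 0.95^(A−1))/0.0513

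Adding six years of later starters, the pooled value is (R + 6 × 0.80)/(N + 6).

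| Earliest start | A | N | R | Pre-2014 starters alone, R/N | All patients | True |
|---|---|---|---|---|---|---|
| 2012 | 2 | 1.676 | 1.580 | 94.3% | 83.1% | 80% |
| 2009 | 5 | 3.789 | 3.693 | 97.5% | 86.8% | 80% |
| 2005 | 9 | 6.146 | 6.050 | 98.4% | 89.3% | 80% |

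Next, starts go back nine years, the earlier start rate is equal to or half the later one, and later annual retention is 90% or 95%. Pre-2014 starters then make up 28-53% of the data. A true 70% reads 77.5-83.0%, a true 80% reads 85.5-89.3%, and a true 90% reads 93.0-95.0%.

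**Between models.** Take two models with identical true retention of 80%, with pre-2014 starters making up 70% of one and 30% of the other:

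- 0.7 × 0.984 + 0.3 × 0.80 = 92.9%
- 0.3 × 0.984 + 0.7 × 0.80 = 85.5%

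The false difference is about 7 points (about 11 at a true 70%, about 4 at a true 90%). Within start period the two models agree in this example, at 98.4% in both and 80% in both, so adjusting for start period returns a difference of zero. The inflated 98.4% remains.

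**Other origins.** A simulation of 600,000 patients under the base case with nine years of earlier starts gave:

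- From 1 January 2014, among earlier starters then in care: 93.9% in the 2014+ sample and 93.9% among all who ever started.
- From model entry in 2016 or later: 95.0% and 95.0%.

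Neither origin is biased by this rule. The second describes the alternative models. Conventional care is different: a pre-2014 starter would normally have entered it before 2014, so with a model-entry origin that arm stays truncated.

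**Remedies.** In the same simulation, the uncorrected 12-month figure from ART start was 89.4%. Restriction to starters from 1 January 2014 gave 80.1%, and delayed entry from that date also gave 80.1%.

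**The case against.** The strongest reply is that the protocol never says retention runs from ART start. The origin may be defined in a statistical analysis plan that is not shown, and an origin common to all arms in 2014 or later is free of this bias. The entry rule also suits its stated purposes: it captures everyone in care for the coverage outcomes and gives a pre-intervention period. Patients lost before 2014 could not have met DSD at scale. All of this stands. What remains is that the stated rule and the stated estimator together give a wrong retention figure under two natural origins, and nothing in section 7c excludes them.

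A second reply is that adjustment would deal with the comparison. Section 7c adjusts for imbalances that are found, and time on ART is among the characteristics to be described by model. In the example above, adjusting for start period removes the false difference entirely. That also stands, but the adjustment is conditional and leaves the levels inflated.

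Third, the list of visit dates does not say that pre-2014 visits will be extracted. That is true. However, an ART start date and one contact in the window are enough to count someone as retained at month 12.

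A reader might infer that retention is inflated by construction, and unevenly across models. The documents do not support this. The origin is open, and different shares of pre-2014 starters by model are plausible, since alternative models have focused on stable patients, but they are not stated. The direction is open too. An ART-start origin favours whichever model has more early starters, while a model-entry origin would tend to flatter conventional care. Nor does the rule require being still in care: anyone who lapsed and returned in the window is included.

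**Conclusion.** The point holds conditionally. The entry rule left-truncates patients who started ART before 2014, and the described analysis of Outcome 9 has no step for it. If retention is counted from ART initiation, or from entry to conventional care before 2014, early retention is overstated. With an assumed true 80% at 12 months from ART start, the reading is about 83% when starts go back to 2012 and about 89% when they go back to 2005. A false difference between models also needs unequal shares of pre-2014 starters and no adjustment for start period or time on ART. At an illustrative 70% against 30%, it is about 4 to 11 points over true 12-month retention of 90% down to 70%. These sizes rest on assumed attrition, assumed start dates and no return to care; returners would change them. This is a cheap improvement to the plan and does not make the entry rule wrong for the coverage outcomes.

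**What to change.** In section 7c, for Outcome 9, add:

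- State the time origin for retention.
- Estimate retention from ART initiation only in patients who initiated on or after 1 January 2014, or use delayed entry from that date.
- Let earlier starters contribute only from a date on or after 1 January 2014 on which they are in care, adjusting for time on ART at that date. Their first recorded contact in the window is a natural choice, because inclusion itself depends on a contact.
- Count no 6-month interval that ends before 1 January 2014.
- Apply the same rule in every model, including conventional care.

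Pre-2014 starters stay in the descriptive and coverage outcomes. The change needs a few sentences and a filter on the ART start date, which section 6b already collects. The downside is fewer patients in the from-initiation estimate, a small loss of precision with up to 1,000,000 records.

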based ART provision for all patients will be called the "conventional" model and will be considered a single model of care. All other models of care will collective be called "alternative" models. A health system that optimizes the provision of approaches will offer one or more alternative models of care for all ART patient populations,

stratified on the basis of criteria ranging from setting (e.g. rural v urban) to risk factors (MSM v young women), patient characteristics (age, sex, condition), to clinic capacity. In this taxonomy, the conventional model of care may serve a specific group of patients—those who require additional services—and it is thus a differentiated model in itself.

In Malawi, the Ministry of Health (MOH) and its implementing partners are currently supporting the scale-up of several alternative models of care ART patients who are stable on ART. These include amongst others, multi month dispensing, fast track refills, nurse led community ART and adolescent centric treatment groups. While some specific DSD models have been or are being evaluated[7-10], there has not yet been an assessment of the reach or impact of DSD at national scale.

b. Rationale

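### Data are collected from 2014 for a pre-intervention comparison, but no specified analysis uses that period or calendar time, so secular trend could be mistaken for a DSD effect in Outcomes 9-11

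*Protocol*

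**What the plan says.** Protocol Section 6a gives the reason for the early start of the data. It states that "The focus countries began large-scale implementation of DSD in 2015 or 2016" and that starting in 2014 "will thus allow us a pre-intervention period for comparison". Section 5b sets the matching inclusion rule, "Patients accessing care for HIV within the data collection period (January 1, 2014 to February 28, 2021"), with no exclusions.

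Section 3a defines the comparator. The original clinic-based provision is called the conventional "model and will be considered a single model of care". It is not divided by period.

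Section 7c describes the analysis for each group of outcomes:

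- Outcomes 1-4 are described by model and by patient characteristics.
- Outcomes 5-6 are checked against operating procedures.
- Outcome 7 is costed.
- Outcome 8 is mapped.
- Outcomes 9-11 (retention, viral suppression and other health outcomes) go through four steps. First, "we will conduct a crude analysis comparing the proportion of subjects with the outcome by model of care". Second, an analysis "accounting only for clustering using generalized estimating equations (GEE) with an unstructured correlation matrix and clustering by treatment site". Third, "should any imbalances between models of care be detected, we will adjust for those covariates in our GEE model". Fourth, stratified analyses by baseline characteristics, of which the examples are "size of the treatment population, rural vs. urban, province, etc".

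**The concern.** The protocol gives a design reason for the 2014 data and then specifies no analysis that acts on it. None of the analyses in Section 7c is a before/after comparison, an interrupted time series or a difference-in-differences, and none names calendar year.

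The consequence goes beyond an unused promise. Care given before scale-up fits the definition of conventional care, and nothing in the protocol keeps outcomes from that time out of the conventional group. If they enter it, conventional outcomes are on average older than DSD outcomes. Any system-wide change between 2014 and 2021, for example in regimens, access to viral load testing or completeness of records, would then be mixed with model of care. An improving trend would favour DSD and a worsening one would count against it.

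This matters for Outcomes 9-11 because Section 7c treats them as contrasts between intervention and comparison arms and speaks of effects of the models. Section 3b itself expects little room for short-term improvement in health outcomes, so a bias of a few points could rival any real difference.

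**Working it through.** **Step 1. Sections side by side.** Section 6a promises a pre-intervention comparison. Section 7c contains description, agreement with procedures, costing, mapping and between-model contrasts. The first two steps for Outcomes 9-11 have no time term. The third names no covariates and acts only on a detected imbalance. The examples in the fourth are not temporal. Among the characteristics listed for description in Section 7c, time on ART appears, but that is not calendar time.

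**Step 2. Share of the window before scale-up.** January 2014 to February 2021 is 7 × 12 + 2 = 86 months.

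- Scale-up from the start of 2015: 12/86 = 14.0%.
- Scale-up from the start of 2016: 24/86 = 27.9%.

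**Step 3. Illustrative size.** The protocol states no figure to reproduce. The following are assumptions, not taken from the documents: the DSD share of patients rises linearly from 0 at the start of scale-up to U = 30-70% in February 2021; cohort size is constant; each patient-month is classified by current model; DSD has no true effect; outcomes change by the same number of points per year in everyone. Then

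spurious risk difference = annual trend × (mean calendar time of DSD follow-up − mean calendar time of conventional follow-up).

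Worked case, scale-up from the start of 2015 and U = 30%, with time in years from January 2014:

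- Total DSD weight: 0.30 × 74/2 = 11.1 months. Conventional weight: 86 − 11.1 = 74.9 months.
- Mean DSD time: 1 + (2/3) × 74/12 = 5.11 years.
- Mean conventional time: (86 × 3.583 − 11.1 × 5.11)/74.9 = 3.36 years.
- Gap: 1.75 years. Pre-scale-up share of conventional time: 12/74.9 = 16%.

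Across the scenarios:

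| Scale-up starts | U | Gap, all months (years) | Gap, pre-scale-up months dropped (years) |
|---|---|---|---|
| 2015 | 30% | 1.75 | 1.21 |
| 2015 | 50% | 1.95 | 1.37 |
| 2015 | 70% | 2.19 | 1.58 |
| 2016 | 30% | 2.09 | 1.01 |
| 2016 | 50% | 2.27 | 1.15 |
| 2016 | 70% | 2.49 | 1.32 |

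Multiplying the gap by the assumed trend gives these spurious differences:

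- 0.5 points per year: 0.9 to 1.2 points.
- 1 point per year: 1.8 to 2.5 points.
- 2 points per year: 3.5 to 5.0 points.

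With the pre-scale-up months dropped, 1.0 to 1.6 points remain at 1 point per year, because uptake keeps rising through the rest of the window.

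**Step 4. Size against precision.** Section 7a foresees up to 1,000,000 individuals. With an assumed 100,000 per group and 90% with the outcome, the 95% half-width is 1.96 × √(2 × 0.9 × 0.1/100,000) = 0.26 points, ignoring clustering. Clustering would widen this, but a modest trend could still look like a clear effect.

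**The case against.** The strongest reply is that the bias is not prescribed by the protocol, and several parts of that reply stand.

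- A reader might infer that all pre-DSD years fall into the conventional group by construction. The documents do not say so. Section 7c compares proportions of subjects, not person-time, and gives no rule for patients who change model. Classifying patients as ever or never in DSD would put the early years of later DSD patients into the DSD group, which is a different bias. Section 6a dates only large-scale implementation, and for the focus countries together, so earlier small-scale use in Malawi is not excluded.
- A reader might also infer that outcomes are pooled over 2014-2021. No section states this. Table 1 in fact limits patient-months enrolled to the preceding 12 months, though that does not concern Outcomes 9-11.
- The imbalance step could pick up calendar time, since its covariates are left open and the relevant dates are collected (Section 6b). Naming covariates is often left to a statistical analysis plan, which is not at hand.
- A figure of 36 months (36/86 = 42%) before DSD would need scale-up to begin only at the end of 2016.
- A site-level before/after analysis is a design choice. It needs site start dates, and Section 6a says the national electronic system does not fully capture model of care.

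Two things survive. The mismatch between Sections 6a and 7c is internal to the protocol and is not a matter of missing detail. And Section 7c does fix the sequence of steps: two have no adjustment at all, and the third is conditional on a detected imbalance. Even if calendar time were adjusted for, years with almost no DSD patients offer no concurrent comparison, so adjustment there rests on the model alone. The reply that the study is descriptive does not help, because Section 7c says that in connection with Outcomes 1-4.

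**Conclusion.** The point holds in a limited form. Section 6a justifies the 2014 data by a comparison that Section 7c does not contain, and calendar time is named nowhere in the analysis. If pre-scale-up outcomes enter the conventional group, secular trend can be mistaken for an effect of DSD in Outcomes 9-11. That this will happen is not established.

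The period at issue is about 14-28% of the window, given scale-up at the start of 2015 or 2016. The size and direction of any bias depend on a trend that the documents do not give. About 2 points for each point per year is an illustration under assumed linear uptake and classification by current model, not an estimate for this study. The change is worth making but is not critical.

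**What to change.** 1. For Outcomes 9-11, define an index date and limit the between-model contrast to index dates in periods when DSD was in use.
2. Within that contrast, match, stratify or adjust by calendar half-year, fixed in advance and applied whether or not an imbalance is detected. Dropping 2014 alone is not enough, as the remaining gap in Step 3 shows.
3. Reconcile Section 6a with Section 7c. Either specify the pre/post comparison, for example a site-level before/after analysis of retention and suppression where DSD start dates can be derived, or remove the rationale.

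The cost is slightly more analysis and fewer conventional records in the contrast. The visit, viral load and DSD participation dates are already among the fields in Section 6b. The pre/post option also requires deriving site start dates, partly from paper files; removing the rationale costs nothing.
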